(Amended 11 July, 2005) (Amended 10 August, 2005)

viii. Outcome Variables

1. Clinical outcome variables

a) Primary clinical outcome variable

The experience of having at least one episode of clinical malaria in the second year of life *detected by passive case detection.* (Amended 2 December, 2004)

b) Secondary clinical outcome variables

1. Fever (axillary temperature \geq 37.5° C or a history of fever in the previous 24 hours)

2. Hct during first, second and subsequent malaria infections, and during the **24 months** cross-sectional surveys.

3. Density of parasitemia during first, second and subsequent malaria infections, and during the **24** *months* cross-sectional surveys.

4. Time to first clinical episode during the second year of life *detected by passive case detection*.

5. Number of clinical episodes during the first year of life *detected by active or passive case detection*.

6. Number of clinical episodes during the second year of life *detected by passive case detection*. (Amended 2 December, 2004)

2. Immunological outcome variables

a) Primary immunological outcome variables:

 Anti-*Pt*EMP1 antibodies in peripheral blood, as measured at 0, 5, 10, 12, 15, 20 and 25 2.5, 5.5,
10.5, 15 and 24 months of age. The outcome variable to be compared between the cohorts will be: -Antibody units converted from median fluorescence intensity [31]

2. Level-Magnitude and frequency of cytokines (IFN- γ , IL-10) in peripheral blood in response to *in vitro* stimulation with Pf parasite antigens, as measured at 0, 5, 10, 12, 15, 20 and 25 2.5, 5.5, 10.5, 15 and 24 months of age

3. Ratio of Th1 (IFN- γ , TNF α , IL-12 and IL-2) to Th2 (IL-10, IL-5, IL-4) cytokines in plasma, as measured at 0, 5, 10, 12, 15, 20 and 25 **2.5, 5.5, 10.5, 15 and 24** months of age.

4. Anti-GPI antibodies in peripheral blood as measured at 2.5, 5.5, 10.5, 15 and 24 months of age. The outcome variables to be compared between the cohorts will be: -Antibody units converted from ELISA titre -Antibody units converted from Functional Neutralization Assay.

Final protocol: 2nd July 2004 Amendment 1: 15th October 2004 Amendment 2: 2nd December 2004 Amendment 3: 11th July 2005 Amendment 4: 10th August 2005 Amendment 5: 12th September 2006 CONFIDENTIAL

Page 24 of 51

CSI/CISM

5. Host genetics:

-Presence of homozygote or heterozygote for each particular SNP. -Presence or absence of nominated haplotype for each gene.

(Amended 11 July, 2005) (Amended 10 August, 2005)

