The incidence of clinical malaria in study participants during the first year of the study was lower than expected. The sample size of the study was thus increased to n=350 total participants in order to increase the power of the study. (Amended 12 September, 2006)

Final protocol: 2nd July 2004 Amendment 1: 15th October 2004 Amendment 2: 2nd December 2004 Amendment 3: 11th July 2005 Amendment 4: 10th August 2005 Amendment 5: 12th September 2006

CONFIDENTIAL

Page 26 of 51

x. Immunological Studies

1. Distribution of blood samples and prioritization

Heparin: 0.5ml cytokine intrac 1-1.5 ml Whole blood EDTA: 0.5-1ml 1-1.5 mL to separate, cryopres	0.25 ml IL-10 (Th2)
Plasmas:	Packed red and white blood cells
Flow cytometry: anti-PfEMP1 ELISA: anti-MSP1, AMA-1, EBA-175, GPI Cytometric bead array or equivalent (IFN-γ, IL-10, TNF-α, IL-5, IL-4, IL-2, IL-12) IFAT: IgG isotypes, IgM Oxidative stress markers Functional Neutralization Assay (GPI, hem Archiving at CISM	Flow cytometry Genotyping host (only at birth) , Hgb AF Genotyping parasite (if parasitemic) Oxidative stress markers Cytokines, Archiving at CISM ozoin)

(Amended 11 July, 2005) (Amended 10 August, 2005)

Samples collected will be aliquoted at the CISM laboratory and frozen. Part of the samples will be assayed for immunological studies at the CISM and part will be sent in batches to the following collaborators to be processed at their laboratories:

-Centre de Salut Internacional, Hospital Clínic, Barcelona, Spain: frozen plasma samples will be sent to them, to be assayed for P. falciparum antibodies and extracellular cytokines.

-Blood Research Laboratories, University of Oxford, UK: frozen plasma samples will be sent to them, to be assayed for anti-haemozoin antibodies and biochemical oxidative stress markers

- Dept. Genetics, Biology and Biochemistry, Università di Torino: frozen plasma and pellet samples will be sent to them, to be assayed for oxidative stress markers

- Immunogenetics Research Group, Univ. Western Australia, Perth, Australia: frozen pellet (PBMCs and RBCs) will be sent to them to determine host genetic factors.

- The Walter and Eliza Hall Institute of Medical Research, Parkville, Australia: frozen plasma samples will be sent to them to be assayed for anti-GPI antibodies.

The remaining aliquots will be stored at CISM to be assayed for determinations contemplated in this protocol.

(Amended 10 August, 2005)

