Genetic data will be analyzed with respect to both intermediate and clinical outcomes. For each genotype examined, plasma specific antibody levels will be compared between homozygotes and heterzygotes within each of the three cohorts (to detect genetic influences within each study group) and between each of the cohorts (to detect genetic influences on differences in outcome caused by varying timing of anti-malarial treatment). In addition, to provide data to contribute to understanding the mechanism of action of NAI, for the genes for $IFN-\gamma$, IL-10, $TNF-\alpha$, IL-4, and IL-12, plasma levels of each of these genes products will be compared between homozygotes and heterzygotes within each cohort and between each of the three cohorts (to detect genetic influences on differences in gene output (and hence serum levels) caused by varying timing of anti-malarial treatment). Similar analyses will be undertaken for other intermediate variables including hematological variables and intracellular staining assays. Genotype will also be analyzed with respect to clinical outcomes at each of the time points of data collection. In these analyses, appropriate correction will be made for multiple analyses.

(Amended 11 July, 2005)

e) Analysis and interpretation of oxidative stress data

Parameters for anti-oxidant potential of the host and for oxidative stress will be compared between cohorts in the cross-sectionals to analyse differences in the development of immune responses to malaria in correlation to risk of clinical malaria attributable to age of first exposure to P. falciparum infection (Amended 11 July, 2005)

xii. Potential Difficulties

1. The location of the study site (40 km from Manhiça) poses logistical difficulties, namely the efficient transport of children (i.e., those requiring admission to the Manhiça Hospital), study personnel, equipment, and samples between Ilha Josina and Manhiça. A large phase IIb trial with the RTS,S candidate malaria vaccine has been recently conducted in Ilha Josina by CISM. Therefore the team already has experience in dealing with all these logistical problems and there are trained field and health workers based there. We believe that the benefits of working with this population in Ilha Josina outweigh the logistic difficulties. We will be increasing the capabilities of the Ilha Josina Health Center and will also have continuously accessible personnel on call in Ilha Josina. (Amended 15 October, 2004)

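### Host-genetic comparison is set as homozygotes versus heterozygotes, without separating the two homozygotes or naming the variant allele

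*Protocol*

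**What the plan says.** Section C makes the study of host genetic factors secondary aim 3. Section D.viii.2.a, item 5, lists host genetics among the primary immunological outcome variables in two lines: "Presence of homozygote or heterozygote for each particular SNP" and "Presence or absence of nominated haplotype for each gene".

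Section D.xi.2.d gives the analysis. For every genotype examined, "plasma specific antibody levels will be compared between homozygotes and heterzygotes within each of the three cohorts", and a comparison between cohorts follows. For the IFN-γ, IL-10, TNF-α, IL-4 and IL-12 genes, "plasma levels of each of these genes products will be compared between homozygotes and heterzygotes within each cohort" and between cohorts. The approach is then carried further: "Similar analyses will be undertaken for other intermediate variables including hematological variables and intracellular staining assays". For clinical outcomes the coding is left open: "Genotype will also be analyzed with respect to clinical outcomes at each of the time points of data collection". On multiplicity the section adds: "In these analyses, appropriate correction will be made for multiple analyses".

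Neither section names a reference or variant allele, an additive, dominant or recessive model, or a three-genotype comparison. The haplotype line in D.viii is not tied to the contrast in D.xi.2.d. Section D.xii, item 8, acknowledges reduced power only for alleles of low frequency.

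**The concern.** At a SNP with alleles A (common) and B (variant) the genotypes are AA, AB and BB. If allele B raises or lowers an antibody level, AA and BB usually lie at opposite ends and AB lies between them. Putting AA and BB together and setting them against AB averages the two extremes, so the contrast can shrink or disappear although the allele has a real effect. If only one homozygote is intended, the third genotype drops out and the contrast cannot see some modes of inheritance.

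The loss falls where the protocol does not warn of it. D.xii expects difficulty with rare alleles, whereas the pooled contrast is weakest for alleles near 0.5, where a cohort of this size would otherwise be most informative. A null result there could be taken as no genetic influence when the comparison had little chance of showing one.

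**Working it through.** The protocol gives no effect size, power or sample size for the genetic comparison, so there is no stated figure to reproduce.

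**Inputs**
- Cohort size: section D.ix says "The sample size of the study was thus increased to n=350 total participants". With three cohorts, 350/3 = 116.7, taken as 117 per cohort with no loss to follow-up.
- Assumptions not in the protocol: Hardy-Weinberg proportions p², 2pq and q² (p = 1 − q, where q is the variant allele frequency); an additive effect a per allele, set at 0.5 SD for power; q from 0.05 to 0.5; two-sided 0.05 with no multiplicity correction.

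**Reading 1: the two homozygotes are pooled**

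Means under an additive effect: AA = 0, AB = a, BB = 2a.

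Pooled homozygote mean = 2a·q²/(p² + q²).

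Contrast = a − 2a·q²/(p² + q²) = a(p² − q²)/(p² + q²) = a(p − q)/(p² + q²), because p + q = 1.

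Information per infant is 2pq(p² + q²) × contrast² for the two-group comparison and 2pq·a² for the 0/1/2 trend. Relative efficiency = (p − q)²/(p² + q²).

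| q | Contrast | Efficiency | Power, pooled | Power, 0/1/2 trend |
|---|---|---|---|---|
| 0.1 | 0.8/0.82 = 0.98a | 0.64/0.82 = 78% | 53% | 63% |
| 0.2 | 0.6/0.68 = 0.88a | 0.36/0.68 = 53% | 60% | 86% |
| 0.3 | 0.4/0.58 = 0.69a | 0.16/0.58 = 28% | 43% | 94% |
| 0.4 | 0.2/0.52 = 0.38a | 0.04/0.52 = 8% | 17% | 96% |
| 0.5 | 0 | 0% | 5% | 97% |

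At q = 0.05 the powers are 35% and 38%. Power is for a = 0.5 SD and 117 infants in one cohort, by normal approximation.

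Other modes of inheritance, with a 1 SD effect and 117 infants:
- Recessive: the size of the contrast is q²/(p² + q²). At q = 0.2 this is 0.04/0.68 = 0.06 SD (power 6%); at q = 0.3 it is 0.09/0.58 = 0.16 SD (power 13%).
- Dominant: the contrast is p²/(p² + q²). It falls from 0.81/0.82 = 0.99 SD at q = 0.1 (power 98%) to 0.50 SD at q = 0.5 (power 72%). Coding by carriage of the variant keeps 99% to 100%.

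**Reading 2: only one homozygote is meant**
- AA versus AB: under an additive effect the contrast is a − 0 = a, with no attenuation. BB is discarded, a share q² of infants (4% at q = 0.2, 25% at q = 0.5). At q = 0.5 with 0.5 SD per allele, power is 60% against 97% for the trend. Under a recessive effect AA and AB have the same mean, so power is 5%, which is chance.
- BB versus AB: under a dominant effect these two have the same mean, so power is again 5%.

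**The case against.** The strongest reply is that the protocol never says the two homozygotes are pooled. It states no coding and no test. The phrase may be shorthand for comparing genotypes, and the line in D.viii may only list what is recorded. Beside the haplotype line it could also mean variant homozygote or heterozygote, with non-carriers as an unstated reference. Elsewhere the protocol speaks generally of genotypes and alleles (D.xii, item 8), and the choice of genetic model often belongs in a statistical analysis plan. This stands to the extent that pooling is the literal reading and not a declared intention. It does not remove the point: D.xi.2.d states the same two-class contrast twice, extends it to other variables, and matches D.viii, and no passage supplies the missing distinction.

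Four stronger conclusions that a reader might draw are not supported:
- That no version of the contrast tests the variant allele. Common homozygote versus heterozygote does estimate a one-copy effect, without attenuation under an additive model.
- That the effect vanishes for common alleles in general. Under pooling and additivity it is exactly zero only at q = 0.5; at q = 0.3 the contrast is still 0.69a, and at q = 0.1 little is lost. A dominant effect keeps much of its power.
- That differences in genetic effect between cohorts go unexamined. D.xi.2.d plans a between-cohort comparison for that purpose and does not say it will rest on setting separate within-cohort results side by side.
- That the clinical-outcome analyses carry the same fault. The genotype coding for those is not stated.

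**Conclusion.** The point holds as a badly fixed comparison: three genotypes are described as two classes, and each literal way of forming those classes has a cost. Under pooling, an additive effect is estimated at 0.98a down to 0 as q goes from 0.1 to 0.5, with efficiency from about 78% to 0%. With one homozygote dropped, an additive effect is not attenuated, but infants are discarded and either a recessive or a dominant effect becomes undetectable.

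The sizes depend on Hardy-Weinberg proportions and on allele frequencies, effect sizes and genetic models that the protocol does not give. The powers are illustrations for one full cohort of 117; losses and a multiplicity correction would lower them.

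The reach is limited to the intermediate-variable genetic analyses under secondary aim 3. The primary clinical comparison, the trial's sample size and the data collected are untouched.

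**What to change.** Reword D.viii.2.a.5 and D.xi.2.d so that, for each SNP:
- the reference and variant allele are named;
- results are reported for the three genotypes separately;
- the test is by number of variant alleles (0, 1 or 2), unless a dominant, recessive or other model is prespecified for that locus.

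Apply the same coding where D.xi.2.d extends the analysis to haematological variables and intracellular staining, and state the coding for clinical outcomes. Any statistical analysis plan should carry the same definitions.

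The cost is a change of wording in two sections. The planned genotyping already distinguishes the three genotypes, so no new samples, assays or participants are needed.

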The primary aim of the study is to determine the effect of timing of exposure to Pf erythrocytic stage antigens during infancy (0 to 5 vs 5 to 10 months of age) on subsequent morbidity due to clinical malaria. The primary outcome variable was chosen as the presence or absence of at least one episode of clinical malaria during the second year of life **as detected by passive case detection**, because current epidemiological data suggests that this outcome is a sensitive, inverse indicator of NAI; when used as the primary outcome variable in studies detailed earlier in this proposal (see background and rationale sections) significant differences were detected between cohorts receiving differing prophylaxis [1, 2]. In the study site, an incidence of **0.4 0.48**-episodes of clinical malaria per person year at risk ([name], personal communication). Thus, as described in the sample size section, each of the three cohorts will be compared to the others in pairwise fashion, with the p value for significance reduced to 0.017 to adjust for the three comparisons. **(Amended 15 October, 2004) (Amended 2 December, 2004)**

However, other variables could also affect the likelihood of experiencing at least one clinical episode during the second year of life, such as number of clinical episodes experienced during the first year of life, regardless of the age at which they occurred. In addition, we believe that immunological responses during the first year of life may potentially explain the differences in susceptibility to clinical episodes during the second year (secondary aim), although other factors, such as host genotype (e.g., presence or absence of sickle cell trait, α -thalassemia or others), the presence of haemoglobin AF, parasite genotype, and possibly maternal immune responses, could also affect the primary outcome variable. Because we do not know which of these many factors will be most closely associated with the outcome, we propose a logistic regression analysis to make this assessment. All of these factors will be used in a multiple logistic regression model, and those with significant associations will be identified. Although it is by no means assured, we hope that one of the immunological measurements (see below) will show a significant association and thus will serve as a positive or negative correlate with NAI. A rationale has been provided regarding the concentration of antibody responses to PfEMP-1 as a likely candidate.

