-Antibody units converted from ELISA titre (titer log₂(titer/10)+1 with reference to last dilution causing positive ELISA as compared with non-specific background and the ratio of IgM, IgG1, IgG2, IgG3 + IgG4 isotypes as measured in the same way)

-Antibody units converted from Functional Neutralization Assay.

(Amended 11 July, 2005)

c) Analysis and interpretation of cellular immunoassays

- The **cytokine intracellular staining** of whole blood will provide information about Pf antigen specific expression of IFN- γ and IL-10 in peripheral blood, the phenotype of the lymphocyte population expressing each cytokine (produced by CD4 or CD8 T cells), as well as the status of activation (CD69 marker) of the cells. Data will be acquired by flow cytometry and analyzed using the CellQuestTM software. Results will be expressed as frequency (%) of cytokine positive CD4+ or CD8+ T cells, and mean fluorescence intensity. For statistical analysis, data on the mean frequency of cytokine expression will be compared between cohorts by t-test or regression analysis; p<0.05 will be considered statistically significant.

- The concentration of unknown cytokines (IFN- γ , IL-10, TNF- α , IL-5, IL-4 and IL-2 and IL-12) in plasma is calculated in the Cytometric Bead Array (CBA) or equivalent via extrapolation from a curve of known standards. Standard curves are plotted [cytokine calibrator concentration vs. FL-2 mean fluorescence intensity] using a 4-parameter logistic curve fitting model. Cytokine concentrations (pg/ml) are determined from these standard curves. If the plasma has a cytokine concentration below the detection limit for the assay, a value of 0 will be assigned. All data will be presented as mean \pm standard error. In addition, cytokine ratios will be calculated to determine the Th1 vs. Th2 balance of cytokines.

Final protocol: 2nd July 2004 Amendment 1: 15th October 2004 Amendment 2: 2nd December 2004 Amendment 3: 11th July 2005 Amendment 4: 10th August 2005 Amendment 5: 12th September 2006 CONFIDENTIAL

Page 35 of 51

Results will be analyzed using the manufacturer's software. Data will be analyzed by a general linear model analysis of variance (ANOVA) with pre-planned comparisons to generate two-tailored p-values. Fisher least significant-difference tests will be used to make appropriate post ANOVA comparisons.

d) Analysis and interpretation of immunogenetic data

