6. Parasite diversity in the region of Ilha Josina- *Manhiça*. We will do parasite genotyping with each clinical episode of malaria. We also have data from previous studies on the most prevalent *P. falciparum* strains circulating in the community. **(Amended 15 October, 2004)**

7. Transmission rate. We have assumed this to be stable, although there may well be some seasonal variations. We will be using block randomisation with open enrolment over a one year period to address this possibility.

8. Genetic factors and other factors of susceptibility and resistance. We will assess for the presence of HgbS, Hgb AF and α -thalassemia in the population, factors that we think could have a profound impact upon host morbidity and mortality. However, we have limited our evaluation of host genetic factors because of our small sample size and blood volumes. Host genetic factors: We will assess both intermediate and disease phenotypes for associations with genotypes in specific genes that we have selected for study. The relatively small population being studied will reduce the chance of finding significant associations for alleles with a low population frequency. (Amended 11 July, 2005)

9. Many *It is possible that some* deliveries will take place at home and not in the maternity. In these cases it will not be possible to take samples or blood from the placenta or cord blood, thus these data will be missing. Peripheral blood from the mother and child will be obtained a few days after delivery. (Amended 15 October, 2004) (Amended 10 August, 2005)

10. For those infants aged 0-2 months enrolled after birth the data from the parasitological and immunological status at birth will be missing. Peripheral blood from the child will be obtained when they are enrolled at the 2,5 months cross-sectional sampling. (Amended 2 December, 2004) (Amended 11 July, 2005)

Final protocol: 2nd July 2004 Amendment 1: 15th October 2004 Amendment 2: 2nd December 2004 Amendment 3: 11th July 2005 Amendment 4: 10th August 2005 Amendment 5: 12th September 2006

CONFIDENTIAL

Page 37 of 51

CSI/CISM

E. HUMAN SUBJECTS RESEARCH

Protection of Human Subjects

1. Risks to the Subjects

a) Human Subjects Involvement and Characteristics

Volunteer Selection:

a) Infants aged 0-2 months, identified in the community

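### For antibody, cytokine and other intermediate outcomes, genotype is compared within each cohort with no pooled cohort-adjusted effect, and the between-cohort step has no named test

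*Protocol*

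**What the plan says.** Protocol section D.xi.2.d (immunogenetic data) sets two comparisons for each genotype. The first is that "plasma specific antibody levels will be compared between homozygotes and heterzygotes within each of the three cohorts". The same sentence continues: "and between each of the cohorts (to detect genetic influences on differences in outcome caused by varying timing of anti-malarial treatment". The same pair is planned for the plasma products of five cytokine genes, and similar analyses follow for other intermediate variables, namely blood-count measures and intracellular staining results. On clinical endpoints the section adds: "Genotype will also be analyzed with respect to clinical outcomes at each of the time points of data collection". It closes with: "In these analyses, appropriate correction will be made for multiple analyses".

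Four other places bear on this:

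- Section C, Secondary Aim 3, asks which host genetic factors influence the development of immunity in early life. It is not tied to a cohort.
- Section D.xi.1.a lists host genotype among the factors that may affect the primary clinical outcome and states: "All of these factors will be used in a multiple logistic regression model, and those with significant associations will be identified". A similar logistic analysis is planned for haematocrit below 25%.
- Section D.xi.2.c says of plasma cytokines: "Data will be analyzed by a general linear model analysis of variance (ANOVA) with pre-planned comparisons". It mentions no genotype term.
- Section D.xii, item 8, concedes: "The relatively small population being studied will reduce the chance of finding significant associations for alleles with a low population frequency".

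**The concern.** Two questions are in play. Aim 3 asks whether a variant influences the immune response at all. The natural answer is one genotype effect estimated on every infant, adjusted for randomised cohort. The second question is whether that influence depends on the timing of treatment. This is a question of interaction, answered by testing whether the genotype effects differ between cohorts.

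For intermediate outcomes the only genotype contrast spelled out is the within-cohort one. It answers the first question three times over, each time with a third of the infants, in a trial that already concedes limited power for low-frequency alleles. The second question is assigned to a between-cohort comparison with no stated test. At stake are missed genetic effects on the intermediate phenotypes. There is also a risk that a variant significant in one cohort and not in another is taken as evidence of timing-dependent genetics.

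**Working it through.** **Inputs.** From the protocol: 350 participants in total (section D.ix, last amendment), equal allocation to three cohorts (section D.iii), 20% loss to follow-up and alpha 0.05 two-sided (section D.ix). Assumed, because the genetic section gives no sample size, power or effect size: the variance explained by a variant, the standardised effect, and the share of heterozygotes.

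**1. The plan's own figure.** The only sample-size figure is clinical. With rates 0.4 and 0.8, alpha 0.017 and 80% power, n = (2.387 + 0.842)² × (0.4 + 0.8) / 0.4² = 78.2, and 78 / 0.80 = 97.5, i.e. 98. This reproduces the stated 78 and 98 per cohort. It says nothing about genetics, and the total has since been raised to 350.

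**2. Evaluable infants.** 350 / 3 ≈ 117 per cohort, and 117 × 0.80 ≈ 94. Three cohorts give 282.

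**3. Precision.** A pooled test uses three times the infants of a within-cohort test, so the ratio of standard errors is √3 = 1.73.

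**4. Power of one test at alpha 0.05.** For a variant explaining a share R² of variance, the non-centrality is λ = n × R² / (1 − R²), with 1 numerator df.

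| R² (assumed) | Within one cohort, n = 94 | Pooled, cohort-adjusted, n = 282 |
|---|---|---|
| 3% | λ = 2.91, power 39% | λ = 8.72, power 84% |
| 5% | λ = 4.95, power 60% | λ = 14.84, power 97% |

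**5. The same check as a heterozygote-versus-homozygote contrast.** With 280 evaluable infants (350 × 0.80) and 30% heterozygotes, the effect detectable with 80% power is 0.63 SD within a cohort and 0.37 SD pooled. Ranges below cover heterozygote shares from 10% to 50%.

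- Effect 0.5 SD: power 60% (31% to 68%) within a cohort, 97% (71% to 99%) pooled.
- Effect 0.3 SD: power 26% (14% to 31%) within a cohort, 63% (33% to 71%) pooled.

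**6. Allowing for three attempts.** The within-cohort approach has three chances to find the variant. In 20,000 simulated trials (93 infants per cohort, 28 of them heterozygous), with each within-cohort test at 0.05/3, the chance of at least one significant cohort was 36% at 0.3 SD and 80% at 0.5 SD. The pooled test at 0.05 gave 63% and 97%. The loss remains.

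**7. If significance were compared across cohorts.** With the same true effect in all three cohorts and within-cohort power p, the three tests disagree with probability 1 − p³ − (1 − p)³. For p = 0.60 this is 1 − 0.216 − 0.064 = 72%; for p = 0.39 it is 1 − 0.059 − 0.227 = 71%. In the simulation at 0.5 SD it was 73%, while the 2-df interaction test rejected in 5%. These figures use uncorrected alpha 0.05. With 20 variants (an assumption) and Bonferroni over 60 within-cohort tests, power at R² = 3% falls to about 5% and the same formula gives 1 − 0.05³ − 0.95³ = 14%.

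**8. Precision of the interaction.** The difference between the genotype effects of two cohorts has standard error √2 times the within-cohort one, so √2 × √3 = 2.45 times the pooled one.

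**The case against.** The strongest reply is that the protocol does plan a between-cohort comparison and states its purpose, which is the question an interaction test answers. This stands. A reader might infer from the within-cohort clause alone that separate p-values have been chosen in place of an interaction test, so that chance patterns will be reported as timing-dependent genetics. The text does not support that: the test is unnamed, nothing says that p-values will be set against each other, and a multiplicity correction is promised. The disagreement figures in step 7 are therefore conditional, and are not error rates of the plan.

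A reader might also infer that no combined genotype effect is planned anywhere, or that the plan discards two thirds of its information. Neither holds. Genotype enters one logistic model for the primary clinical outcome, with a similar one for haematocrit, and the clinical-outcome sentence in D.xi.2.d carries no within-cohort restriction. All three cohorts are analysed. The loss of two thirds describes a single within-cohort test.

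The logistic model does not cover antibodies or cytokines, however. It also enters genotype alongside immune responses, through which genotype may act, so it would not give the total genotype effect.

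Finally, model form often belongs in a statistical analysis plan, and the general linear model named for cytokines could carry both terms. That is a fair reason not to treat the unnamed test as an error. It does not remove the main point: the protocol itself states the within-cohort contrast, and a better analysis of the same data is available.

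**Conclusion.** The point holds for intermediate outcomes only. As written, each stated genotype test there uses one third of the infants, and no cohort-adjusted pooled effect is planned to answer Secondary Aim 3. The factor of 1.73 in the standard error follows from equal allocation to three cohorts. The power figures also rest on about 94 evaluable infants per cohort, alpha 0.05 and the assumed effect sizes.

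Misreading cohort differences is a possibility only if the unspecified between-cohort step is done by comparing significance. This is an inexpensive improvement to a secondary-aim analysis, although section D.viii.2.a lists host genetics among the primary immunological outcomes. The primary clinical comparison is not touched.

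**What to change.** Amend section D.xi.2.d so that, for each variant and intermediate outcome:

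1. The main test is the genotype effect in a model with genotype and cohort, fitted to all infants.
2. The planned between-cohort comparison is a 2-df genotype-by-cohort interaction test, and dependence on treatment timing is claimed only from it.
3. Within-cohort estimates are shown with confidence intervals, descriptively.
4. The promised multiplicity correction is applied to the pooled and interaction tests.

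The cost is wording; no further samples or data are needed. The downside is that the pooled effect averages over cohorts. The interaction test that checks this has limited power (step 8), so a non-significant interaction should not be read as proof that the effect is the same in all cohorts.
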